### **Major clinical response**

Major clinical response is defined as continuous six-months of ACR70 response for a subject.

### **DAS28, low disease activity and remission**

The Disease Activity Score (DAS) is a combined index to measure the disease activity in patients with RA. It has been extensively validated for its use in clinical trials in combination with the EULAR response criteria.

The DAS28 is a measure of disease activity based on Swollen and Tender Joint Counts, CRP or ESR, and the Patient Global Assessment of PsA disease activity.

The following 28 joints will be assessed for tenderness and swelling: metacarpophalangeal IV (10), thumb interphalangeal (2), hand proximal interphalangeal II-V (8), wrist (2), elbow (2), shoulders (2), and knees (2).

The following formulas can be used to calculate the DAS28 with CRP (mg/L) or ESR (mm/hour).

$$\text{DAS28-CRP} = 0.56 * \text{sqrt}(\text{TJC28}) + 0.28 * \text{sqrt}(\text{SJC28}) + 0.36 * \ln(\text{CRP}+1) + 0.014 * \text{PGA} + 0.96$$

[figure not shown]
$$\text{DAS28-ESR} = 0.56 * \text{sqrt}(\text{TJC28}) + 0.28 * \text{sqrt}(\text{SJC28}) + 0.70 * \ln(\text{ESR}) + 0.014 * \text{PGA}$$

[figure not shown]
*TJC28: 28 Tender joint count; SJC28: 28 Swollen joint count; CRP: C-reactive protein; PGA: Patient Global Assessment*

If any component measurement is missing, DAS28 will be missing.

DAS28-CRP will be primarily used for the interpretation of the outcome; DAS-ESR is considered supportive.

DAS28-CRP (or ESR) remission is defined as a DAS28-CRP (or ESR) index score less than 2.6. Low disease activity is defined as DAS28-CRP (or ESR) index less than or equal to 3.2.

## **ACR Components**

### ***Tender 78 joint count and swollen 76 joint count***

The 78 joints assessed for tenderness include the 2 temporomandibular, 2 sternoclavicular, 2 acromioclavicular joints, 2 shoulders, 2 elbows, 2 wrists, 2 first carpometacarpal, 10 metacarpophalangeal, 10 proximal interphalangeal, 8 distal interphalangeal joints of the hands, the 2 hip, 2 knee, 2 talo-tibial, 2 mid-tarsal, 10 metatarsophalangeal, 10 proximal interphalangeal, and 8 distal interphalangeal joints of the feet. All of these except for the hips are assessed for swelling. Joint tenderness and swelling are to be graded present (1) or absent (0). Synovial fluid and/or soft tissue swelling but not bony overgrowth represents a positive result for swollen joint count. Dactylitis of a digit in the foot or hand counts as one tender and swollen joint. These aspects are to be implemented during data capture and will not be addressed during programming.

If the number of joints for which data were available (e.g., T) is less than 78/76 for the tender/swollen joint assessment, the number of tender/swollen joints (e.g., t) will be scaled up proportionately (i.e.,  $78*t/T$  or  $76*t/T$  for tender or swollen joint count).

### ***Patient's assessment of PsA Pain***

The patient's assessment of pain will be performed using 100 mm visual analog scale (VAS) ranging from "no pain" to "unbearable pain" after the question "*Please indicate with a vertical mark (|) through the horizontal line the most pain you had from your psoriatic arthritis today*".

### **Patient's global assessment of disease activity**

The patient's global assessment of disease activity will be performed using 100 mm VAS ranging from "very good" to "very poor", after the question "*Considering all the ways psoriatic arthritis affects you, please indicate with a vertical mark (|) through the horizontal line how well you are doing today*".

### **Physician's global assessment of PsA disease activity**

The physician's global assessment of disease activity will be performed using 100 mm VAS ranging from no disease activity to maximal disease activity, after the question "*Considering all the ways the disease affects your patient, draw a line on the scale for how well his or her condition is today*". To enhance objectivity, the physician must not be aware of the specific patient's global assessment of disease activity, when performing his own assessment on that patient.

### **Erythrocyte sedimentation rate (ESR)**

[figure not shown]
Blood for ESR, which is helpful in diagnosing inflammatory diseases and is used to monitor disease activity and response to therapy, will be obtained at scheduled visits.

### **High-sensitivity C-reactive protein (hsCRP)**

Blood for this assessment will be obtained in order to identify the presence of inflammation, to determine its severity, and to monitor response to treatment. Since the results of this test may unblind study personnel, results from the central lab will be provided for screening and baseline only. The hsCRP results from samples collected during the treatment period will be revealed following database lock only.

### **Radiographic assessments**

See Section 2.12.4.1 on Joint/bone structural damage for a description of the derivation of the vdH-mTSS.

### **Presence of enthesitis**

If enthesitis is present with any of the 6 sites (lateral epicondyle humerus L + R, proximal achilles L + R and medial condyle femur L + R), the patient is counted as a patient with enthesitis.

### **Dactylitis count**

The dactylitis count is the number of fingers and toes with dactylitis based on the LDI, with a range of 0-20.

### **Presence of dactylitis**

If dactylitis according to the LDI is present with any finger or toe, the patient is counted as a patient with dactylitis.

### **Psoriasis Area and Severity Index (PASI)**

The PASI assessment will be conducted for subjects in whom at least 3% of the body surface area (BSA) was affected by psoriatic skin involvement at baseline (Psoriasis Subset). The PASI assesses the extent of psoriasis on four body surface areas (head, trunk and upper and lower limbs) and the degree of plaque erythema, scaling and thickness. A PASI score will be derived as indicated in [Table 2-7](#). The head, trunk, upper limbs and lower limbs are assessed separately for erythema, thickening (plaque elevation, induration), and scaling (desquamation). The average degree of severity of each sign in each of the four body regions is assigned a score of

0-4. The area covered by lesions on each body region is estimated as a percentage of the total area of that particular body region. Further practical details help the assessment:

1. The neck is assessed as part of the head.
2. The axillae and groin are assessed as part of the trunk.
3. The buttocks are assessed as part of the lower limbs.
4. When scoring the severity of erythema, scales should not be removed.

**Table 2-7 The PASI scoring system**

Body region	Erythema (E)	Thickening (plaque elevation, induration, I)	Scaling (desquamation) (D)	Area score (based on true area %, A)*
Head (H)**	0=none 1=slight 2=moderate 3=severe 4=very severe	0=none 1=slight 2=moderate 3=severe 4=very severe	0=none 1=slight 2=moderate 3=severe 4=very severe	0 = no involvement 1 = >0-< 10% 2 = 10-<30% 3 = 30-<50% 4 = 50-<70% 5 = 70-<90% 6 = 90-100%
Trunk, (T)***	0=none 1=slight 2=moderate 3=severe 4=very severe	0=none 1=slight 2=moderate 3=severe 4=very severe	0=none 1=slight 2=moderate 3=severe 4=very severe	0 = no involvement 1 = >0-< 10% 2 = 10-<30% 3 = 30-<50% 4 = 50-<70% 5 = 70-<90% 6 = 90-100%
Upper limbs (U)	0=none 1=slight 2=moderate 3=severe 4=very severe	0=none 1=slight 2=moderate 3=severe 4=very severe	0=none 1=slight 2=moderate 3=severe 4=very severe	0 = no involvement 1 = >0-< 10% 2 = 10-<30% 3 = 30-<50% 4 = 50-<70% 5 = 70-<90% 6 = 90-100%
Lower limbs (L)****	0=none 1=slight 2=moderate 3=severe 4=very severe	0=none 1=slight 2=moderate 3=severe 4=very severe	0=none 1=slight 2=moderate 3=severe 4=very severe	0 = no involvement 1 = >0-< 10% 2 = 10-<30% 3 = 30-<50% 4 = 50-<70% 5 = 70-<90% 6 = 90-100%

Percentage (not score) of body region (not whole body) affected will be entered in the eCRF

\*\*Neck is assessed as part of the Head (H) body region.

\*\*\*Axillae and groin are assessed as part of the Trunk (T) body region.

[figure not shown]
\*\*\*\*Buttocks are assessed as part of the Lower limbs (L) body region.

[figure not shown]
Because the head and neck, upper limbs, trunk and lower limbs correspond to approximately 10%, 20%, 30% and 40% of the body surface area, respectively, the PASI score is calculated using the formula:

[figure not shown]
$$\text{PASI} = 0.1(E_H + I_H + D_H)A_H + 0.2(E_U + I_U + D_U)A_U + 0.3(E_T + I_T + D_T)A_T + 0.4(E_L + I_L + D_L)A_L$$

[figure not shown]
The keys for the letters are provided in [Table 2-7](#).

[figure not shown]
PASI scores can range from a lower value of 0, corresponding to no signs of psoriasis, up to a theoretic maximum of 72.0. The total score comes from eCRF.

## **2.13 Interim analysis**

The primary endpoint analysis will be performed after all subjects have completed the Week 24 visit. The investigators, site personnel and monitors will continue to remain blinded to the treatment each subject received at randomization until database lock for Week 52 analysis.

Subsequent to the primary endpoint analysis, additional analyses are planned for regulatory submission and/or publication purposes after subjects have completed the Week 52 assessments. The final analysis will be conducted after all subjects complete the study. Additional analyses may be performed to support interactions with health authorities, as necessary.

## **3 Sample size calculation**

A 5% two-sided type I error rate will be used to control for type I error. Three secukinumab regimens will be tested versus placebo with respect to the primary endpoint (ACR20 response at Week 24), thus the type-I-error will be split to 1.67% two-sided for each comparison. Sample sizes will be based on this type I error assumption. With an assumed placebo rate of 15% and secukinumab 51% (FUTURE 2), the study is over 99% powered to detect a treatment difference of ACR20 in the FAS population, assuming 220 subjects in a secukinumab treatment group, and 330 subjects in the placebo group (Fisher's exact test, nQuery 7.0). This power is applicable for all three dose regimens, as the sample size is driven by structural endpoint.

Power for secondary variables was calculated using a two-sided 1.67% type I error. With an assumed placebo rate of 7% and secukinumab 35% (FUTURE 2), the study is over 99% powered to detect a treatment difference of ACR50 in the full FAS population, assuming 220 subjects in a secukinumab treatment group, and 330 subjects in the placebo group (Fisher's exact test, nQuery 7.0).

For structural endpoint, historical data (FUTURE 1) showed a standard deviation of 1.132 on active treatment and 2.435 on placebo at Week 24, and a difference of 0.52. Using the above assumptions, there is 83% power to show statistically significant differences assuming 220 subjects in a secukinumab group and 330 subjects in the placebo group (Satterthwaite t-test, nQuery 7.0).

A standard deviation of approximately 0.49 and a treatment difference of 0.17 has been observed for the change from baseline at Week 24 in HAQ-DI® (FUTURE 2). Using those assumptions, the study has approximately 94% power to detect a difference between secukinumab and placebo (Two group t-test, nQuery Advisor 7.0), assuming 220 subjects in a secukinumab treatment group and 330 subjects in the placebo group.

For the presence of dactylitis at Week 24 in the subset of subject who have dactylitis at BSL, with an assumed placebo rate of 85% and secukinumab 50% (FUTURE 2), there is about 99% power to show statistically significant difference between secukinumab (110) and placebo (165 subjects), assuming 50% subject have dactylitis at BSL (Fisher's exact test, nQuery 7.0).

For the presence of enthesitis at Week 24 in the subset of subject who have enthesitis at BSL, with an assumed placebo rate of 79% and secukinumab 58% (FUTURE 2), there is about 94% power to show statistically significant difference between secukinumab (132 subjects) and

placebo (198 subjects), assuming 60% subjects have enthesitis at BSL (Fisher's exact test, nQuery 7.0).

With an assumed placebo rate of 16% and secukinumab 48% (FUTURE 2), the study is over 99% powered to detect a treatment difference of PASI75 in the FAS population, assuming 110 subjects in a secukinumab treatment group, and 165 subjects in the placebo group. It is assumed that about 50% of enrolled subjects have  $\geq 3\%$  skin involvement.

A difference of 0.62 and standard deviation of 1.04 has been observed for the change from baseline in DAS28-CRP (FUTURE 2). With these assumptions, the study has over 99% power to detect a difference between secukinumab and placebo (Two group t-test, nQuery Advisor 7.0), assuming 220 subjects in a secukinumab treatment group, and 330 subjects in the placebo group.

A standard deviation of approximately 7.19 and a treatment difference of 4.44 has been observed for the change from baseline at Week 24 in SF36-PCS (FUTURE 2). Using those assumptions, the study has over 99% power to detect a difference between secukinumab and placebo (Two group t-test, nQuery Advisor 7.0), assuming 220 subjects in a secukinumab treatment group, and 330 subjects in the placebo group.

With an assumed placebo rate of 9% and secukinumab 33% (FUTURE 2), the study is over 99% powered to detect a treatment difference of PASI90 in the FAS population, assuming 110 subjects in a secukinumab treatment group, and 165 subjects in the placebo group. It is assumed that about 50% of enrolled subjects have  $\geq 3\%$  skin involvement.

## **4 Appendix**

### **4.1 Visit Windows and Cut-off Dates**

#### **4.1.1 Visit windows**

When visit windows are used, all visits will be re-aligned, i.e., they will be mapped into one of the visit windows. E.g., if the *Week 4* visit of a subject is delayed and occurs on Day 46 instead of on Day 29, say, it will be re-aligned to visit window *Week 8*. In the case of major deviations from the visit schedule, or due to unscheduled visits, several assessments of a subject may fall in a particular visit window (either scheduled or unscheduled). Statistical approaches to handle multiple assessments in a given visit window are specified in [Table 4-2](#).

For lab/ECG/vital signs, follow-up (F/U) visit is excluded from analysis visit mapping window. Only assessments that come as F/U nominal visit will be directly assigned as analysis F/U visit. Other assessments that are beyond the last on-treatment visit window (W104) or after nominal F/U visit date won't be mapped to any analysis visit. F/U visit will not be included in the summary tables by visit.

Of note, subjects are allowed to have gaps in visits. All data collected will be displayed in listings.

**Table 4-1 Analysis visit windows**

The following rules are used to determine the window for an applicable visit post baseline: “Lower limit” = “upper limit of prior applicable visit” + 1. “Upper limit” = “target day of current visit” + integer part of (“target day of next applicable visit” – “target day of current visit”)/2. Lower limit of the first applicable visit is always Day 2. Day 1 is the date of the first dose of randomized study treatment

The mapping described above applies to all visits (not just scheduled visits). Repeat and/or unscheduled visits (which will be numbered in the database according to new NCDS standards) will be mapped for analysis purposes in the same way as scheduled visits. This leaves the possibility, then, for multiple measurements within an analysis window. The following conventions will be used to determine the appropriate measurement to be summarized in the event of multiple measurements within a visit window.

**Table 4-2 Rules for flagging variables**

Timing of measurement	Type of data	Rule
Baseline	All data	
The last non-missing measurement made prior to or on the date of administration of the first dose of study treatment (the reference start date / Day 1). If a patient did not receive any dose of study treatment then the randomization date will be used. Only date part is considered if just one assessment on Day 1.
 
If there are multiple assessments on Day 1, following rules will apply:
 

a. If assessment time exists,

• select the last available measurement prior to reference start date/time considering time;

• if no measurement prior to reference start date/time considering time, select the earliest measurement post reference start date/time considering time .

b. If assessment time does not exist, select the available measurement from the lowest CRF visit number.

 
For X-ray, a baseline value is the last measurement prior to dosing if available. Otherwise, take the first value within 30 days post dosing.
 
For MRI, a baseline value is the last measurement prior to dosing if available. Otherwise, take the first value within 7 days post dosing.

Post-baseline efficacy	All data	
For visits without switch of treatment in the window, the measurement closest to the target will be used. In the event two measurements are taken equally apart (e.g. 1 before target date and 1 after) the first one will be used.
 
For visits during which the patient switches from placebo to AIN the following will be done based on whether or not the patient met the rescue criteria:
 

• If the analysis visit window is <= week 16(for non-responders) or week 24 (for responders), then:

Timing of measurement	Type of data	Rule
		

• If available, the closest measurement to the target date which is ON or BEFORE the switch date will be used (i.e. the closest measurement to target which is on placebo).

• If there are no data on or before the switch then the closest measurement to the target date after the switch will be used.

• If the analysis visit window is > week 16(for non-responders) or week 24 (for responders), then

• If available, the closest measurement to the target date which is AFTER the switch date will be used (i.e. the closest measurement to target which is on AIN).

• If there are no data AFTER the switch then the closest measurement to the target date before the switch will be used.

 
Cases where the same parameter is recorded more than once on the same date will be handled as follows:
 

• If time of completion exists the earliest measurement will be used;

• If time does not exist the measurement from the lowest CRF visit number will be used.

Post-baseline safety	Summary visit information (e.g. lab, ECG, etc.)	
For visits without switch of treatment in the window, the measurement closest to the target will be used. In the event two measurements are taken equally apart (e.g. 1 before target date and 1 after) the first one will be used.
 
For visits during which the patient switches from placebo to AIN the following will be done based on whether or not the patient met the rescue criteria:
 

• If the analysis visit window is <= week 16(for non-responders) or week 24 (for responders), then:

• If available, the closest measurement to the target date which is ON or BEFORE the switch date will be used (i.e. the closest measurement to target which is on placebo).

• If there are no data on or before the switch then the closest measurement to the target date after the switch will be used.

• If the analysis visit window is > week 16(for non-responders) or week 24 (for responders), then

• If available, the closest measurement to the target date which is AFTER the switch date will be used (i.e. the closest measurement to target which is on AIN).

• If there are no data AFTER the switch then the closest measurement to the target date before the switch will be used.

Timing of measurement	Type of data	Rule
		Cases where the same parameter is recorded more than once on the same date will be handled as follows: 

• If time of completion exists the earliest measurement will be used;

• If time does not exist the measurement from the lowest CRF visit number will be used.

Post-baseline safety	Notable abnormalities (e.g. lab)	The most extreme measurement in the window will be used. Note this means a patient can have a notably high and notably low measurement within a window.

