9.4.3 Handling of missing values/censoring/discontinuations

Missing data for ACR20 response and other binary efficacy variables (e.g. ACR50, ACR70, HAQ-DI[®] response, etc.) for data up to Week 24 will be handled as follows:

- Subjects who drop out of the trial for any reason will be considered non-responders from the time they drop out through Week 24.
- Subjects who do not have the required data to compute ACR response (i.e. tender and swollen joint counts and at least three of the five ACR core set variables) at BSL and at the specific time point will be classified as non-responders.

Continuous variables (e.g. ACR components, DAS, etc.) will be analyzed using a mixed-effects repeated measures model (MMRM) which is valid under the missing at random (MAR) assumption. For analyses of these parameters, if all post-BSL values are missing then these missing values will not be imputed and this subject will be removed from the analysis of the

[figure not shown]
corresponding variable, i.e. it might be that the number of subjects providing data to an analysis is smaller than the number of subjects in the FAS.

Data collected after Week 24 will generally be presented as 'observed case'; i.e. all available data for each time point will be included in the analyses.

In general, the handling of data for subjects who are rescued at Week 16 will be handled in the following fashion for comparisons with placebo at Week 20 and Week 24:

- For each binary endpoint, a subject will be considered as a non-responder at Week 20/24 for that endpoint if the subject is a non-responder (including missing imputed non-responder) at Week 16. If a subject is a responder at Week 16, the actual value at Week 20/24 will be used (missing is considered as non-responder). This will be done for all treatment regimens in order to minimize bias.
- For continuous endpoints, the goal of the analyses would be to estimate what would have happened if the subjects had stayed on the original treatment. Thus, the data collected after the subject switches to secukinumab will be treated as missing for placebo subjects and will be analyzed using a MMRM which is valid under the missing at random (MAR) assumption. For secukinumab subjects, the actual values will be used in the analysis.

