### **Missing data**

Missing data for ACR20 response for data up to Week 16 will be handled as follows:

- Subjects who drop out of the trial for any reason will be considered non-responders from the time they drop out through Week 16.
- Subjects who do not have the required data at baseline and at the specific time point to compute response will be classified as non-responders.

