## **Rescued patients**

[figure not shown]
In general if not stated otherwise (as e.g. for vdH-mTSS), the handling of data for subjects who are **rescued at Week 16** will be handled in the following fashion for comparison with placebo at Week 20 and Week 24:

[figure not shown]
For each binary endpoint, a subject will be considered as a non-responder at Week 20/24 for that endpoint if the subject is a non-responder (including missing imputed non-responder) at Week 16. If a subject is a responder at Week 16 for that endpoint, the actual value at Week 20/24 will be used (missing is considered as non-responder). This will be done for all treatment regimens in order to minimize bias.

[figure not shown]
- For continuous endpoints, the goal of the analyses would be to estimate what would have happened if the patients had stayed on the original treatment. Thus, the data collected after a Placebo patient switches to secukinumab will be treated as missing for the placebo group and will be analyzed using a mixed-effects repeated measures model (MMRM) which is valid under the missing at random (MAR) assumption. For secukinumab patients that are rescued, the actual values will be used in the analysis.

[figure not shown]
Data collected **after Week 24** will generally be presented as ‘observed case’; i.e. all available data for each time point will be included in the analyses. In addition, multiple imputation will be used for long-term (e.g. after week 52) comparison for selected endpoints.

For comparisons between the active arms the rescue penalty will not be applied as the effect of rescuing is the same for both treatment groups (i.e. the patient continues to receive secukinumab 150 mg or 300 mg every 4 weeks).

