### **Handling of rescued/early escape patients data**

Two scenarios might be observed:

Subjects following the original protocol who are non-responder at Week 16 (not achieving a  $\geq 20\%$  improvement from baseline in both TJC and SJC) will have their hands/wrists and feet X-rays taken at Week 16 and no additional X-ray at week 24.

Subjects following the amendment 1 of the protocol who are non-responders at week 16 are expected to have both a week 16 and week 24 X-ray taken.

All subjects (irrespective of the protocol version) who are responder at Week 16 ( $\geq 20\%$  improvement from baseline in both tender and swollen joint counts) will have their hands/wrists and feet X-rays taken at Week 24.

For patients receiving rescue therapy (who meet the criteria for early escape at Week 16) their week 24 X-ray assessment will be treated as missing for placebo treatment and linear extrapolation will be used to impute the value at Week 24.

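### SAP Table 4-2 lets a post-switch value stand as the placebo Week 16 or Week 24 efficacy value, and nothing says whether the missing-data rules override it

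*SAP*

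**What the plan says.** SAP 4.1.1 maps each assessment to an analysis window, and Table 4-2 selects the value that represents the visit. The post-baseline efficacy row covers all efficacy data and has a special branch for placebo subjects who switch during a window. The branch applies to windows up to "week 16(for non-responders) or week 24 (for responders), then" the value closest to target on or before the switch date is taken, which the table explains as the closest one on placebo. Failing that: "If there are no data on or before the switch then the closest measurement to the target date after the switch will be used".

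Other sections say what happens when a visit has no usable value:

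- **Binary endpoints** (SAP 2.6.3, Missing data, and 2.5.3 for ACR20): "Subjects who do not have the required data at baseline and at the specific time point to compute response will be classified as non-responders". The PASI, enthesitis and dactylitis estimands in SAP 2.6.2.2 are built on this.
- **Continuous endpoints** (SAP 2.6.3, Rescued patients): the aim is the outcome had the patient stayed on the randomized treatment, so "the data collected after a Placebo patient switches to secukinumab will be treated as missing for the placebo group". Protocol 9.4.3 agrees: "the data collected after the subject switches to secukinumab will be treated as missing for placebo subjects".
- **mTSS** (SAP 2.6.2.2): the estimand supposes that early escape was not open to placebo patients. For rescued placebo patients, SAP 2.12.4.1 says "their week 24 X-ray assessment will be treated as missing for placebo treatment", and SAP 4.2.7.1 extrapolates Week 24 from the Week 16 film.

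Neither document says whether Table 4-2 or these rules prevail.

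**The concern.** A value is selected for a visit before missing-data rules are applied. Once Table 4-2 has filled the visit, nothing is missing, so non-responder imputation, MMRM and extrapolation have nothing to act on. A measurement made on secukinumab is then analysed in the placebo group at the visit that is meant to show the placebo effect.

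The exposed hierarchy endpoints are PASI75, PASI90, HAQ-DI, DAS28-CRP, enthesitis and dactylitis at Week 16, and mTSS at Week 24. mTSS can be reached in two ways: a rescued subject's post-switch film serving as the Week 16 film that feeds the extrapolation, or a placebo responder's post-switch film serving as the Week 24 film. There is a plausible route. Protocol 6.4.2 foresees repeat films after central quality control, and the switch dose may already have been given by then. The Amendment 1 rationale expects about 66% of placebo subjects to be Week 16 non-responders (0.66 × 330 ≈ 218), so many placebo mTSS values depend on the Week 16 film. mTSS also drives the sample size and has the lowest stated power, 83%.

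**Working it through.** **1. Window rule (SAP, Table 4-1 text).** Upper limit = target + integer part of (next target − target)/2; lower limit = previous upper limit + 1. Target day = 7 × week + 1, which matches the SAP's Day 29 for Week 4 and Day 169 for Week 24.

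The SAP's own example first: the Week 4 upper limit is 29 + int((57 − 29)/2) = 43, and the Week 8 window is Day 44 to 57 + int((85 − 57)/2) = 71. A visit on Day 46 therefore maps to Week 8, as SAP 4.1.1 says.

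**2. How late a fallback value can be, for a switch on the target day.**

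| Measures | Week 16 window ends | Days after switch | Week 24 window ends | Days after switch |
|---|---|---|---|---|
| Four-weekly (HAQ-DI, DAS28-CRP) | 113 + int((141 − 113)/2) = 127 | 14 | 169 + int((197 − 169)/2) = 183 | 14 |
| PASI, enthesitis, dactylitis (Protocol Table 6-1: none at Weeks 20 and 28) | 113 + int((169 − 113)/2) = 141 | 28 | 169 + int((225 − 169)/2) = 197 | 28 |

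X-ray windows depend on the body of Table 4-1, which is not shown in the text available.

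**3. What each rule gives for a placebo subject with only a post-switch value in the window.**

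| Endpoint | Section 2.6 | Table 4-2 |
|---|---|---|
| PASI75/90, enthesitis, dactylitis | Non-responder | On-secukinumab value, possibly a response |
| HAQ-DI, DAS28-CRP | By its aim, no value; MMRM under MAR | On-secukinumab value |
| mTSS, rescued, no pre-switch Week 16 film | Escape supposed unavailable | Post-switch film sets the slope |
| mTSS, responder, no pre-switch Week 24 film | Not stated | Post-switch film used as Week 24 |

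**4. ACR20 and ACR50 at Week 16.** Protocol 5.3 withholds the Week 16 kit until responder status is recorded, so joint counts precede the switch. A placebo subject who switches at Week 16 has under 20% improvement in tender or swollen joints. ACR20 needs at least 20% in both (Protocol 6.4.1), and ACR50 needs 50%. A later pain, HAQ or CRP value cannot reverse that. Placebo responders switch at Week 24, outside the Week 16 window.

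**5. Direction and size.** For binary endpoints the existing rule gives non-response, so the fallback can only raise the placebo response rate. For continuous endpoints it moves placebo toward active if secukinumab works. Both are toward no difference.

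The plan's powers at two-sided 0.05/3, with 220 versus 330 subjects:

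- mTSS: SE = √(1.132²/220 + 2.435²/330) = 0.154; 0.52/0.154 = 3.37; Satterthwaite t power 83.3% (stated 83%).
- HAQ-DI: SE = 0.49 × √(1/220 + 1/330) = 0.0426; 0.17/0.0426 = 3.99; power 94.4% (stated 94%).

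The documents give no frequency. As an assumed range, let a fraction f of placebo values take the full active mean (worst case), so that the difference shrinks to (1 − f) of its planned size:

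| f | mTSS power | HAQ-DI power |
|---|---|---|
| 0 | 83.3% | 94.4% |
| 1% | 82.5% | 94.0% |
| 2% | 81.6% | 93.5% |
| 5% | 78.8% | 91.8% |

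**The case against.** The strongest reply is that the fallback will hardly ever operate. Protocol 5.5.4 and 6.4 require assessments before dosing, so a pre-switch value should nearly always exist. That stands, and it limits the size of the point. It does not justify a rule that gives the wrong value when it does operate.

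A reader might infer three stronger things that the documents do not support.

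- **That the primary comparison is contaminated.** Step 4 of the working shows that it should not be, given that the joint counts behind the responder call are in the database.
- **That Table 4-2 flatly contradicts the post-switch missing-data rule.** That rule concerns continuous endpoints in subjects rescued at Week 16, whose data "will be handled in the following fashion for comparison with placebo at Week 20 and Week 24", and it opens "In general if not stated otherwise (as e.g. for vdH-mTSS"). The fallback acts at Week 16 for those subjects and at Week 24 for placebo responders, whose post-switch data no section expressly sets to missing. What remains is conflict with the stated aim and estimands, conflict with non-responder imputation for binary endpoints, and an unstated order of precedence.
- **That a film taken months after the switch could count as placebo Week 24.** If X-ray windows used only X-ray visits, the Week 24 window would end on Day 169 + int((365 − 169)/2) = 267, which is 98 days after the switch. This rests on a table body that cannot be seen. SAP 4.1.2 also cuts the Week 24 analysis at the Week 24 visit number, which would exclude a film filed under a later visit.

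It is also fair to say that setting every post-switch film to missing has a price. Placebo responders have no scheduled Week 16 film (Protocol 6.4.2), so without a Week 24 film they would usually leave the mTSS analysis.

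**Conclusion.** The point holds and is minor. As written, Table 4-2 can put an on-secukinumab value into the placebo group at Week 16 (non-responders) or Week 24 (responders), against the estimands for PASI75/90, enthesitis, dactylitis and mTSS and the stated aim for HAQ-DI and DAS28-CRP. The 14-day and 28-day limits assume a switch on the target day and the visit schedule in Protocol Table 6-1. The power losses are illustrations under an assumed frequency and a worst-case shift, not estimates of what will happen. Because the bias is toward no difference, this mechanism does not favour a false claim of efficacy. The reason to act is that two programmers following the SAP could produce different placebo values.

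**What to change.** - **Clinical efficacy endpoints, placebo comparisons:** delete the fallback from the post-baseline efficacy row. Treat the visit as having no data, so that the existing rules apply: non-responder for binary endpoints, MMRM under MAR for continuous ones.
- **Precedence:** state that SAP section 2.6 overrides Table 4-2.
- **mTSS, rescued placebo subjects:** in the primary analysis, do not let a post-switch film serve as the Week 16 film that feeds the extrapolation.
- **mTSS, placebo responders:** state explicitly how a Week 24 film taken after the switch is handled, and show the alternative as a sensitivity analysis.

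The cost is a few sentences and a few values that become missing. For mTSS, a rescued placebo subject left with no usable post-baseline film would drop out of the primary analysis under SAP 2.6.2.2. Extrapolation Method 2 (SAP 4.2.7.1), which uses all observed Week 24 films, would still include that subject if a Week 24 film exists. Planning power does not change.
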